BLOOM Study

English translation of the original French document.

Research sponsor: Groupe Hospitalier de La Rochelle Ré Aunis

Coordinating investigator: [name] [name]

1. Administrative information

Title/Acronym (will be made public): Real-world data from people with diabetes using closed-loop insulin pump therapy (BLOOM)

Project team: [name] (hospital practitioner) / [name] (PhD) / [name] (clinical research associate)

2. Objectives and purpose

a. Study background and objectives

In recent years, insulin pump systems coupled with continuous glucose sensors enabling semi-automated insulin delivery (closed-loop systems) have been developed.

Their use has been validated in clinical trials, but the international investigation centres participating in these trials are not always representative of French centres, and the patients they manage may also differ. Eligibility criteria in trials are stricter and more restrictive than those in routine practice in diabetology/endocrinology departments. Sociodemographic characteristics of trial participants - notably the male/female ratio, age, and ethnicity - do not necessarily reflect those observed in patients who actually use the device in real-world care.

Our objective is to evaluate, in real-world conditions, the impact of closed-loop systems on improving glycaemic control in people with diabetes managed in diabetology/endocrinology departments of general hospitals.

b. Ethical compliance

The purposes of data processing are defined, explicit and legitimate. An information letter is handed to patients in person or sent by post to their home. The data collected are adequate, relevant, and limited to what is necessary for the study.

c. Public interest justification

This study will measure the effectiveness and risks associated with the use of closed-loop insulin pumps in routine clinical practice.

d. Dissemination and publication

Peer-reviewed scientific article.

3. Methodology

a. Required data sources

- Medical records
- PMSI only
- SNDS extraction
- Registry
- Survey / cohort
- Other: diabetes platforms (CareLink / MyDiabby / YourLoops)

b. Study cohort description

Inclusion criteria:

- Age > 7 years
- Type 1 diabetes
- Equipped with a closed-loop insulin pump

Non-inclusion criteria:

- Presence of a legal protection measure limiting autonomous decision-making
- Patient or legal representative objecting to the use of data for research purposes

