c. Methods, data processing and analysis

Data will be collected as follows:

i. At inclusion (baseline)

- Demographics: sex, age, weight, body mass index (automatically calculated).
- Medical history: retinopathy, nephropathy, coronary artery disease, stroke.
- Diabetes-related data: diabetes duration, HbA1c, year of insulin pump initiation, type of glucose monitoring (continuous glucose monitoring [CGM]; e.g., FreeStyle Libre or other - to be specified), year of CGM initiation.
- Data from the diabetes platform (CareLink) for the 3 months prior to closed-loop initiation and the last 14 days: time in range 70-180 mg/dL (TIR), time below range <70 mg/dL (TBR), time above range >180 mg/dL (TAR), mean glucose, coefficient of variation, mean number of capillary blood glucose tests per day, mean total daily insulin dose, basal/bolus ratio, grams of carbohydrates consumed per day.
- Number of severe hypoglycaemic events in the last 12 months.
- Ketosis or diabetic ketoacidosis in the last 12 months.
- Diabetes-related hospitalisations in the last 12 months.
- Device data: date of closed-loop initiation, closed-loop pump brand (MiniMed), configured glucose target, active insulin time in closed-loop mode.

ii. Follow-up at M3 (3 months after inclusion)

- Clinical characteristics: weight, BMI.
- Data from the diabetes platform for the last 14 days: HbA1c, time in SmartGuard, time in temporary basal, time in manual mode, TIR, TBR, TAR, configured glucose target, mean glucose, coefficient of variation,

mean number of capillary blood glucose tests per day, mean total daily insulin dose, basal/bolus ratio, grams of carbohydrates consumed per day.

- Device data: number of sensors used, number of sensor malfunctions; report transmitter and/or pump change if applicable (MiniMed, t:slim, DBLG1).
- Adverse events: number of severe hypoglycaemic events since the previous visit; number of episodes of ketosis or diabetic ketoacidosis since the previous visit; number of diabetes-related hospitalisations since the previous visit; other diabetes-related adverse events.

iii. Follow-up at M6 (6 months after inclusion)

- Clinical characteristics: weight, BMI.

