- Data from the diabetes platform for the last 14 days: HbA1c, time in SmartGuard, time in temporary basal, time in manual mode, TIR, TBR, TAR, configured glucose target, mean glucose, coefficient of variation, mean number of capillary blood glucose tests per day, mean total daily insulin dose, basal/bolus ratio, grams of carbohydrates consumed per day.
- Device data: number of sensors used, number of sensor malfunctions; report transmitter and/or pump change if applicable (MiniMed, t:slim, DBLG1).
- Adverse events: number of severe hypoglycaemic events since the previous visit; number of episodes of ketosis or diabetic ketoacidosis since the previous visit; number of diabetes-related hospitalisations since the previous visit; other diabetes-related adverse events.

iv. Follow-up at M12

- Clinical characteristics: weight, BMI.
- Data from the diabetes platform for the last 14 days: HbA1c, time in SmartGuard, time in temporary basal, time in manual mode, TIR, TBR, TAR, configured glucose target, mean glucose, coefficient of variation, mean number of capillary blood glucose tests per day, mean total daily insulin dose, basal/bolus ratio, grams of carbohydrates consumed per day.
- Device data: number of sensors used, number of sensor malfunctions; report transmitter and/or pump change if applicable (MiniMed, t:slim, DBLG1).
- Adverse events: number of severe hypoglycaemic events since the previous visit; number of episodes of ketosis or diabetic ketoacidosis since the previous visit; number of diabetes-related hospitalisations since the previous visit; other diabetes-related adverse events.

v. Follow-up at M18 (end of study)

- Clinical characteristics: weight, BMI.
- Data from the diabetes platform for the last 14 days: HbA1c, time in SmartGuard, time in temporary basal, time in manual mode, TIR, TBR, TAR, configured glucose target, mean glucose, coefficient of variation, mean number of capillary blood glucose tests per day, mean total daily insulin dose, basal/bolus ratio, grams of carbohydrates consumed per day.
- Device data: number of sensors used, number of sensor malfunctions; report transmitter and/or pump change if applicable (MiniMed, t:slim, DBLG1).
- Adverse events: number of severe hypoglycaemic events since the previous visit; number of episodes of ketosis or diabetic ketoacidosis since the previous visit; number of diabetes-related hospitalisations since the previous visit; other diabetes-related adverse events.

vi. Analyses

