- Describe demographic and clinical characteristics of the type 1 diabetes population initiated on closed-loop therapy (M0).
- Assess changes in glycaemic control at M3, M6, M12 and M18 versus M0 (TIR, TBR, TAR, HbA1c, mean glucose and glucose coefficient of variation).
- Assess adherence to closed-loop use at M3, M6, M12 and M18 (percentage of time in SmartGuard, manual mode, on closed-loop pump, and reasons for discontinuation).
- Assess changes in insulin requirements at M3, M6, M12 and M18 versus M0 (mean total daily insulin dose, basal/bolus ratio, carbohydrate intake).
- Assess safety (number of diabetes-related hospitalisations, diabetic ketoacidosis, severe hypoglycaemia) and device vigilance (pump/transmitter changes, number of sensors used, defective sensors) at M3, M6, M12 and M18.
- Assess self-monitoring practices at M3, M6, M12 and M18 (mean number of capillary blood glucose tests).

d. Data flow and record linkage

Data will be extracted from the electronic medical record and the closed-loop device software (CareLink, MyDiabby, YourLoops) and entered into an eCRF.

Data in the eCRF will be pseudonymised. The paper correspondence table (re-identification key) will be kept at the investigator site and destroyed after acceptance of the publication.

The database will be transferred to the statistician for analysis via a secure channel. It will then be stored and archived on the clinical research department server.

Only aggregated data will be presented in the study report and scientific publications.

e. Planned timeline and feasibility

- May-August 2022: preparation of study documents, selection of participating centres, and design of the eCRF.
- September 2022: study initiation.
- September 2022-August 2023: retrospective data collection for patients already using closed-loop pumps, and prospective inclusion of patients newly initiated on closed-loop therapy.
- A one-month delay between sending information letters and starting data collection will be respected.
- September 2023-January 2025: follow-up of prospectively included patients.
- February-March 2025: data analysis.
- April-May 2025: manuscript drafting.
- Mid-2025: submission.

4. Privacy, security and confidentiality of data

a. Patient information and protection of rights

Individual information of patients/service users, etc.

Collective information

Data media and security

Request for exemption from individual information (to be justified):

5. References

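### The timeline closes follow-up one month short of the last M18 visits, and baseline is tied to inclusion in some places and to closed-loop initiation in others, which differ for patients already on the device

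*Combined protocol and SAP*

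**What the plan says.** **Dates.** The second data-collection line of section 3.e reads "September 2022-August 2023: retrospective data collection for patients already using closed-loop pumps, and prospective inclusion" of newly started patients. It is followed by "September 2023-January 2025: follow-up of prospectively included patients", then "February-March 2025: data analysis" and "April-May 2025: manuscript drafting". Section 3.c.v makes M18 the final visit: "Follow-up at M18 (end of study". No visit window is given for M18 or any other visit.

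**Time origin.** Section 3.c.i is headed "At inclusion (baseline", and the headings of 3.c.ii and 3.c.iii count M3 and M6 from inclusion. The M12 and M18 headings name no origin. Within 3.c.i, however, the platform data are taken "for the 3 months prior to closed-loop initiation and the last 14 days", and 3.c.vi attaches M0 to the population started on closed loop. The initiation date is one of the items collected at baseline.

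**Who is included.** Section 3.b requires every patient to be "Equipped with a closed-loop insulin pump", and section 3.e takes in both patients already using the device and patients newly started on it. No sentence says what inclusion or M0 means for the first group.

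**The concern.** The main planned analysis is change versus M0 at M3, M6, M12 and M18, so the plan needs one M0 and one visit clock. A patient already on closed loop at inclusion has two candidate origins, and the text supports each in a different place. With inclusion as the origin, any baseline item that has no anchor of its own is measured after treatment has begun. For HbA1c, the change then no longer measures the effect of starting the device. With initiation as the origin, the inclusion-based visit headings are wrong. Centres entering data in the eCRF could resolve this differently.

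The date conflict is separate and simpler. If follow-up closes as scheduled, the last month of prospective inclusions either lacks M18 data or supplies them while the analysis is under way.

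**Working it through.** **1. Dates**

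Inputs: inclusion September 2022 to August 2023, follow-up close January 2025 and analysis from February 2025 (all 3.e); last visit M18 (3.c.v); origin inclusion (3.c.ii and 3.c.iii; applying it to M18 is an inference, since 3.c.v names none).

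- Stated follow-up length: September-December 2023 (4) + 2024 (12) + January 2025 (1) = 17 calendar months after inclusion ends. M18 needs 18.
- M18 date = inclusion date + 18 calendar months, compared with 31 January 2025:

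| Inclusion | M18 | Days after close |
|---|---|---|
| 31 July 2023 | 31 January 2025 | 0 |
| 1 August 2023 | 1 February 2025 | 1 |
| 15 August 2023 | 15 February 2025 | 15 |
| 31 August 2023 | 28 February 2025 | 28 |

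- The stated close is therefore right for inclusion ending on 31 July 2023, not 31 August 2023.
- Share affected: 31 / 365 inclusion days = 8.5%. This is a share of patients only if accrual is even, which the plan does not say.
- With a close on 28 February 2025, 0 of 365 inclusion days miss M18, provided visits fall exactly on time.

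**2. Time origin for already-equipped patients**

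Let k be the months from initiation to inclusion. Because 3.b requires the device at inclusion, k is above zero for this group.

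| Item | Anchor in the text | If k > 0 |
|---|---|---|
| TIR, TBR, TAR, mean glucose, CV, insulin dose, basal/bolus ratio, carbohydrates | Three months before initiation | Pre-treatment |
| The same measures, 14-day window | None stated | Wholly on treatment if counted back from inclusion and k is at least 14 days; pre-treatment if counted back from initiation |
| HbA1c | Only the inclusion heading | On treatment |
| Weight, BMI | Only the inclusion heading | On treatment |
| 12-month event history | None stated | Partly or wholly on treatment if counted back from inclusion |
| M3 and M6 | Inclusion | Occur at k + 3 and k + 6 months of use |

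For illustration, with k = 6 the M3 visit falls at 6 + 3 = 9 months of use. If M18 follows the same clock, it falls at 6 + 18 = 24 months. The visit timing affects every change outcome. The on-treatment baseline affects HbA1c with certainty and the 14-day measures on one reading. Weight and BMI are not listed among the change outcomes in 3.c.vi.

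**3. Does the timeline reveal the intended clock?**

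Section 3.e lists collection for already-equipped patients only up to August 2023. If the clock started at inclusion, the earliest inclusion (1 September 2022) would reach M12 on 1 September 2023 and M18 on 1 March 2024, both after that line ends. The timeline therefore fits an initiation clock better for this group, but no sentence states one.

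**The case against.** The strongest reply is that the authors plainly meant initiation. Retrospective collection makes little sense otherwise, step 3 above points that way, and most glycaemic and insulin outcomes already have a pre-initiation window. Much of this stands. It makes the problem a correction of wording, not a flaw in the design. It does not settle HbA1c, the 14-day window or the visit headings, which say something else.

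On dates, section 3.e is a month-level schedule, the late visits are largely platform downloads and record entries, and they fall in the first of two analysis months. Prospective patients may also have started the device before inclusion. The one-month wait after the information letter could widen that gap. On an initiation clock the shortfall then shrinks, and it disappears if every August 2023 inclusion had started by 31 July 2023. All of this is fair and is why the point is minor. The wait does not move the stated August 2023 end of inclusion.

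A reader might infer three stronger things, none of which the documents support.

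- *The whole change analysis compares on-treatment with on-treatment values.* It does not: the platform measures have a stated pre-initiation window.
- *M18 results would come from earlier starters than M3-M12 results.* This assumes that records of already-equipped patients are cut off at 31 August 2023, whereas 3.e gives a period of collection and not a record cut-off. Nor does it follow for a pooled analysis, because later-starting prospective patients still supply M18.
- *An on-treatment 12-month event history distorts the change results.* Section 3.c.vi assesses safety at each visit without comparing it with M0, so that history enters only the baseline description.

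**Conclusion.** Both conflicts are real. They differ in weight.

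The date error is minor: one of twelve inclusion months, with M18 1-28 days late if visits are counted from inclusion and no window applies. The 8.5% figure rests on even accrual and does not count patients shown to be lost.

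The anchor conflict matters more because it bears on the main analysis. Read as written, already-equipped patients have an on-treatment HbA1c baseline and visits later in treatment than their labels say. Its size cannot be computed: the plan gives no sample size, no split between already-equipped and prospective patients, and no distribution of start dates. The documents also give no basis for the direction or size of any resulting difference.

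**What to change.** **Time origin.**
- Define M0 as the date of closed-loop initiation for all patients, already-equipped and prospective alike, so that the pooled comparison has one M0.
- Count M3 to M18 from that date.
- Take HbA1c, weight and BMI, the 14-day data and the 12-month event history from before it.
- Reword the inclusion-based headings in 3.c.i to 3.c.iii to match, and name the origin for M12 and M18.

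**Dates.**
- State an M18 visit window.
- Run follow-up to at least 28 February 2025 plus that window. That date alone leaves no slack for late visits.
- Move the later lines accordingly. Before any window is added, that means analysis in March-April 2025, drafting in May-June 2025, and submission after that.

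**Extraction and reporting.**
- State that M12 and M18 records of already-equipped patients are extracted up to the same cut-off as those of prospective patients.
- Report the number of patients contributing at each visit.

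**Cost.** About one month on the timeline plus the chosen window, a few sentences of definition, and some further extraction for a number of patients that the plan does not give. The initiation date is already collected, so the M0 definition needs no new variable and can still be fixed at the analysis stage.

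### No follow-up of existing closed-loop users is planned after August 2023, so those who started in about March–August 2022 cannot supply M18, and M12 depends on an unstated extraction date

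*Combined protocol and SAP*

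**What the plan says.** Section 3.e (Planned timeline and feasibility) places two groups in the same year: "September 2022-August 2023: retrospective data collection for patients already using closed-loop pumps, and prospective inclusion of patients newly initiated on closed-loop therapy". The next period covers only one of them: "September 2023-January 2025: follow-up of prospectively included patients". No line provides for data on existing users after August 2023. The section also states: "A one-month delay between sending information letters and starting data collection will be respected". It does not date the letters. Nor does it say when in the year each existing user's record is extracted, or whether it is extracted more than once.

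Section 3.c.vi (Analyses) plans to "Assess changes in glycaemic control at M3, M6, M12 and M18 versus M0", and looks at adherence, insulin requirements, safety and self-monitoring at the same four time points. None of these is restricted to prospective patients, and there is no rule for a visit that a patient has not reached when the data are collected. M0 is linked to the start of treatment, since the population described is the "type 1 diabetes population initiated on closed-loop therapy (M0").

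The visit headings in 3.c use a different origin. The first is "Follow-up at M3 (3 months after inclusion"), and M6 follows the same pattern. M12 has no stated origin, and the last is "Follow-up at M18 (end of study"). Section 3.b sets no minimum time on closed loop, so recent starters are eligible.

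**The concern.** The analyses run to 18 months, but the timeline stops looking at existing users in August 2023. Someone who started closed loop a few months before the study opened has not reached 18 months by then. Their M18 is missing because of the collection calendar, not because they stopped the device or left care.

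Two things are at stake. First, M18 results lose precision although the data would come into existence before the analysis starts in February 2025. Second, the contributors change from visit to visit: M3 and M6 can include recent starters among the existing users, while M18 consists of prospective patients and longer-standing users. A reader comparing the M3, M6, M12 and M18 results would then see a mixture of change over time and change in who is measured. The plan has no missing-visit rule that would deal with this.

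**Working it through.** The plan states no figure on this point, so there is nothing to reproduce. The check is calendar arithmetic.

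**Inputs from section 3.e**
- Retrospective collection of existing users: September 2022 to August 2023.
- Follow-up of prospective patients: September 2023 to January 2025.
- One month between information letter and data collection.

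**Assumptions**
- An existing user is someone on closed loop before September 2022, because those newly initiated from then on are assigned to prospective inclusion.
- The earliest extraction is 1 October 2022, which supposes that letters go out in September 2022.
- Visits are counted from closed-loop initiation, as M0 in 3.c.vi suggests.

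**Rule.** For start date S and extraction date C, visit Mk is available only if S + k months ≤ C. The latest start that still has the visit is therefore C − k months.

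| Extraction date C | Latest start with M12 | Latest start with M18 |
|---|---|---|
| 1 October 2022 | 1 October 2021 | 1 April 2021 |
| 28 February 2023 | 28 February 2022 | 28 August 2021 |
| 31 August 2023 (last possible) | 31 August 2022 | 28 February 2022 |

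**M18.** Even on the last possible day, starts from March to August 2022 have no M18. For them M18 falls between 1 September 2023 (start 1 March 2022) and 29 February 2024 (start 31 August 2022). The latest of these dates is about 11 months before follow-up ends.

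**M12.** The latest existing user (start 31 August 2022) reaches M12 on 31 August 2023, just inside the window. No existing user necessarily loses M12; it is lost only through early extraction without a return to the record. For example, suppose each patient is extracted once, with dates spread evenly over the 335 days from 1 October 2022 to 31 August 2023. A 1 March 2022 starter then has M12 in 184/335 = 55% of cases, a 1 August 2022 starter in 31/335 = 9%, and neither ever has M18.

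**Illustrative size.** Assume that starts are spread evenly over the L months before September 2022. The start months that miss a visit are:
- M18, extraction at end of August 2023: March–August 2022, 6 months, share 6/L.
- M18, extraction on 1 October 2022: April 2021–August 2022, 17 months, share 17/L.
- M12, extraction at end of August 2023: none, share 0.
- M12, extraction on 1 October 2022: October 2021–August 2022, 11 months, share 11/L.

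| L (months) | M18 missing, 6/L to 17/L | M12 missing, 0 to 11/L |
|---|---|---|
| 18 | 33% to 94% | 0 to 61% |
| 24 | 25% to 71% | 0 to 46% |
| 36 | 17% to 47% | 0 to 31% |

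**If visits are instead counted from inclusion.** An existing user included on 1 September 2022 reaches M12 on 1 September 2023 and M18 on 1 March 2024. Data ending in August 2023 would then hold M18 for no existing user and M12 for almost none. The origin therefore has to be settled before the loss can be judged.

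**The case against.** Combining a retrospective group with a prospectively followed group is a legitimate design, and the sponsor may have meant existing users to contribute only what was already on record. The listed analyses compare each visit with M0 and name no comparison between later visits. A within-patient change from M0 is not invalidated because different patients contribute at different visits. The missingness is administrative, set by start date, and nothing in the documents shows that recent starters differ from others. All of this stands. It limits the harm to lost M18 precision and to comparisons across visits, which readers of an M3–M18 series will make even if the plan does not name them.

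Three stronger readings are tempting and unsupported:
- **Each existing user is captured only once.** Section 3.e gives a 12-month window and does not state the number of extractions.
- **Recent starters never reach M12.** Everyone on closed loop before September 2022 reaches it by 31 August 2023, so a late or repeated extraction would recover it.
- **The missing share is 18/L for M18 and 12/L for M12.** Those fractions let starts run right up to the collection date. With collection in August 2023, they would count as existing users people whom the plan assigns to prospective inclusion.

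**Conclusion.** The point holds in a limited form. Section 3.e provides no data on existing users after August 2023. Counted from closed-loop initiation, M18 is therefore unobtainable by design for those who started in about March–August 2022, although it falls inside the study calendar. That conclusion does not depend on the extraction date. Loss of M12, and of M18 for earlier starters, is a risk that depends on an extraction date the plan leaves open.

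The percentages are illustrations resting on evenly spread starts. The documents give neither the number nor the start dates of existing users, so the real size cannot be computed. The changes from M0 planned in 3.c.vi remain interpretable for the patients who contribute; a reader should not infer that they are biased by this. This is an inexpensive improvement in completeness and in comparability between visits, not a flaw that undermines the study.

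**What to change.** In section 3.e, reword the later window along these lines: *from September 2023 to January 2025, follow-up covers all included patients who have not yet reached 18 months after closed-loop initiation, whether identified retrospectively or prospectively.* For existing users, enter the visits already passed at first extraction, then extract the remaining ones from the platform and medical record as they fall due. This makes M12 and M18 reachable for everyone on closed loop before September 2022, the last M18 falling on 29 February 2024.

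In section 3.c, state the visit origin for existing users, so that visits counted from inclusion and an M0 at closed-loop initiation no longer conflict.

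The cost is a revised timeline line, a statement of origin, modest extra data entry for existing users with under 18 months of use, and an information letter that covers the later extraction. The data sources and eCRF are those already named in 3.d, and the re-identification key is kept until the publication is accepted, so records can still be linked. If the sponsor prefers to keep the retrospective group closed, the minimum is to state the extraction date or dates, acknowledge the missing M18, and report the number of contributors at each visit by group.

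A separate matter remains: a patient starting on 31 August 2023 reaches M18 on 28 February 2025, after the window closes. The latest start that reaches M18 by 31 January 2025 is 31 July 2023.
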